5.1 Primary Outcome Measures

- Overall postoperative morbidity rates

5.2 Secondary Outcome Measures

- Intraoperative morbidity rate
- Operative time
- Estimated blood loss
- Number of harvested and metastatic lymph nodes
- the lengths of incision, proximal and distal margins
- Time to first flatus
- Time to first liquid diet
- Postoperative hospital stay
- Total cost

6. Diagnostic criteria for this study

- (1) The AJCC-8th TNM tumor staging system will be used for this study.
- (2) Diagnostic criteria and classification of gastric cancer: According to the histopathological international diagnostic criteria, classification will be divided into

papillary adenocarcinoma (pap), tubular adenocarcinoma (tub), mucinous adenocarcinoma (muc), signet ring cell carcinoma (sig), and poorly differentiated adenocarcinoma (por).

(3) Definition of advanced stage: tumor infiltration of the stomach wall reaches or exceeds the inherent muscular layer (T2); T2, T3, and T4a patients will be included as study subjects, whereas T4b patients will not.

(4) Definition of esophagogastric junction carcinoma: According to the AJCC-8th tumor staging system, esophagogastric junction carcinoma is defined as a tumor whose tumor center is located within 5cm above and below the esophagogastric junction. According to Siewert classification, the tumor was divided into Siewert type I : the tumor center was located 1 ~ 5 cm above the esophagogastric boundary; Siewert type II : The center of the tumor was 1 cm to 2 cm above the esophagogastric boundary. Siewert type III : The tumor center is located 2 to 5 cm below the esophagogastric boundary. Only Siewert type III esophagogastric junction carcinoma were involved in this study.

7 Qualifications of the participated Surgeons

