In 2000, robotic-assisted surgery began to be used in clinical practice. Due to the 3D high-definition images, the elimination of tremor and the flexibility of operation, robotic-assisted surgery has gradually become a frontier and research hotspot in the field of minimally invasive surgery^[12]. In 2003, Hashizume was the first to report the robotic-assisted radical gastrectomy. Since then, many studies and meta-analyses have confirmed that robot-assisted radical gastrectomy can achieve the same short-term and long-term clinical efficacy as laparoscopy^[13-15]. However, at present, most studies on robotic-assisted gastric surgery are on distal gastric cancer, and there are few reports comparing robotic and laparoscopic total gastrectomy. Yoon et al.^[16] retrospectively analyzed 36 patients and 65 patients who underwent robotic and laparoscopic total gastrectomy from 2009 to 2011. There are no significant differences between the two groups in terms of intraoperative blood loss, postoperative hospitalization days, postoperative complications, and the total number of lymph node dissection. However, the study has a certain limitation. These lymph node dissection method are not completely D2 radical resection. Meanwhile, the proportion of patients with early gastric cancer reached 70%. Son et al.^[17] retrospectively analyzed 51 patients and 58 patients who underwent total gastrectomy with robotic and laparoscopic splene-preserving D2 during 2003-2010. The operative time of robotic-assisted surgery group was longer than that of the laparoscopic group, and there were no significant differences between the two groups in intraoperative blood loss, postoperative hospital stay, postoperative first flatus and intake time, postoperative complications, and the total number of lymph node dissection, but more lymph node dissection was performed by the robot at 10 and 11p than by the laparoscope (3.6vs1.9;P =0.014). Meanwhile, there was no significant difference in the 5-year overall survival rate and disease-free survival rate between the two groups, but 70% of the cases were early gastric cancer. The above-mentioned literatures suggests that robotic versus laparoscopic total gastrectomy is safe and feasible, but the number of reported cases is small, and most of them are patients with early gastric cancer. In China, 90% of patients are diagnosed with advanced gastric cancer, and total gastrectomy for advanced gastric cancer is more difficult and has a wider range of lymph node dissection. Therefore, it is more necessary

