4.1 Inclusion criteria

- (1) Age between 18 and 80 years
- (2) Endoscopic biopsy and CT confirmed locally advanced gastric adenocarcinoma, requiring D2 radical gastrectomy.
- (3) Preoperative examination showed no absolute contraindication and no distant metastasis
- (4) Performance status of 0 or 1 on ECOG scale
- (5) ASA class I, II, or III
- (6) Written informed consent

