4.3 Withdraw criteria

- (16) Patients intraoperatively/postoperatively confirmed as T4b
- (17) M1 tumor confirmed intraoperatively or postoperatively: distant metastasis only found by intraoperative exploration or postoperative pathological biopsy or a positive postoperative peritoneal lavage cytology examination
- (18) Requirement of simultaneous surgery for other diseases
- (19) Patients intraoperatively confirmed as unable to complete D2 lymph node dissection/R0 resection due to tumor: unable to complete R0 resection due to regional lymph node integration into a mass or surrounded with important blood vessels, which cannot be resected
- (20) Sudden severe complications during the perioperative period (intolerable surgery or anesthesia), which renders it unsuitable or unfeasible to implement the study treatment protocol as scheduled
- (21) Patients who voluntarily quit or discontinue treatment for personal reasons at any stage after inclusion in this study
- (22) Treatment implemented is proven to violate study protocol.

5. Outcome Measures

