9.1 Case selection

9.1.1 Selection assessment items

Clinical examination data of patients conducted from hospital admission to enrollment into this study (time period is usually 2 weeks) will be considered baseline data, and must include:

- (1) Systemic status: ECOG score, height, weight, BMI, ASA score;
- (2) Peripheral venous blood: Hb、RBC、WBC、LYM、NEU、NEU%、PLT、MONO
- (3) Blood biochemistry: albumin, prealbumin, total bilirubin, indirect bilirubin, direct bilirubin, AST, ALT, creatinine, urea nitrogen, Total cholesterol, triglycerides, fasting glucose, potassium, sodium, chlorine, calcium
- (4) Serum tumor markers: CEA、CA19-9、CA72-4、CA12-5、AFP
- (5) Full abdominal (slice thickness of 10mm or less, in case of allergy to the contrast agent, CT horizontal scanning is allowed only)
- (6) Upper gastrointestinal endoscopic ultrasonography (EUS) and biopsy, if no EUS, select ordinary upper gastrointestinal endoscopy and biopsy instead
- (7) Chest X-ray (AP and lateral views): cardiopulmonary conditions(Chest CT replacement is permitted)
- (8) Resting 12-lead ECG

(9) Respiratory function tests: FEV1, FVC

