9.3.1.3 Intraoperative exploration

Explore the abdominal cavity for any hepatic, peritoneal, mesenteric, or pelvic metastases and gastric serosal invasion

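### Stage found at or after surgery is re-applied at the upper end only: pT4b and M1 patients leave the per-protocol set while pT1 patients stay, although eligibility is on clinical stage

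*Protocol*

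**What the plan says.** **Population.** Section 6(3) defines advanced disease as T2 or deeper and adds that "T2, T3, and T4a patients will be included as study subjects, whereas T4b patients will not". It gives no c or p prefix. The Summary states the indication as cT2-4a, N0/+, M0. Inclusion criterion 2 (section 4.1) is "Endoscopic biopsy and CT confirmed locally advanced gastric adenocarcinoma, requiring D2 radical gastrectomy", and section 9.1.2 requires eligibility to be confirmed before the operation.

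**Preoperative staging.** Section 9.1.1 allows CT slices of up to 10 mm and, for endoscopic ultrasound, "if no EUS, select ordinary upper gastrointestinal endoscopy and biopsy instead".

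**Withdrawal.** Section 4.3, item 16, removes "Patients intraoperatively/postoperatively confirmed as T4b". Item 17 removes M1 found at exploration, on postoperative pathology, or through "a positive postoperative peritoneal lavage cytology examination". Neither section 4.2 nor section 4.3 mentions T1. Item 22 concerns the treatment given, not stage.

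**Lavage.** The exploration step in section 9.3.1.3 reads "Explore the abdominal cavity for any hepatic, peritoneal, mesenteric, or pelvic metastases and gastric serosal invasion" and does not mention lavage. Nor do the operative record (9.3.2) or the postoperative items (9.3.4). The annex does code positive cytology as M1 (16.2.5.3) and as R1 (16.2.5.6.2).

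**Analysis set.** Section 10.1 puts all analyses on a per-protocol basis, and section 9.2 ties withdrawal to removal from that set. Sections 8.1 and 8.1.2 use all operated patients as the denominator, and section 10.1 also names a safety population.

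**The concern.** Take two patients who both met cT2-4a at entry and both had the study operation. One, entered as cT4a, proves to be pT4b and leaves the per-protocol set. The other, entered as cT2, proves to be pT1 and stays. Both were equally eligible, and both staging errors became known only afterwards. The rule therefore trims one tail of the stage distribution and leaves the other.

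The background (section 1) gives this weight. It notes of an earlier robotic comparison "but 70% of the cases were early gastric cancer", describes total gastrectomy for advanced disease as more difficult, and presents the present study as the answer for that disease. A set that drops the most advanced cases and keeps the earliest moves back toward the population that the protocol regards as uninformative.

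Allocation is neither random nor blinded, so both the pT1 share and the number of late withdrawals can differ between arms. The lavage criterion adds to this: if sampling is left to the surgeon, membership of the analysis set can depend on whether a sample was taken.

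**Working it through.** **Inputs from the protocol (section 3.3):** control complication rate 15%, margin 15 points, α = 0.05, β = 0.2, 68 evaluable patients per group, 75 after allowing 10% loss.

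**Assumptions, because the documents give no figures:** the share f of pT1 patients in the analysed set, and the robotic excess in pT1 as a fraction k of the excess in T2-T4a.

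**1. The plan's own figure.** The test declares non-inferiority when (p_R − p_L − 0.15)/√[(p_R(1−p_R) + p_L(1−p_L))/n] ≤ −1.645. Exact binomial enumeration with both rates at 15% gives power 0.800 at n = 68 and 0.786 at n = 67. So 68 is reproduced at one-sided 5%, and this test is used below.

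**2. Effect of pT1 patients on a claim about locally advanced disease.** Set the true excess in T2-T4a equal to the margin (30% against 15%), so a declaration of non-inferiority there is false. With the control rate at 15% in both strata, the robotic rate is 0.15 + 0.15(1−f) + 0.15·k·f. For f = 20% and k = 0 this is 0.15 + 0.12 = 27%, an apparent excess of 12 points.

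False non-inferiority, n = 68 per arm, one-sided 5%:

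| pT1 share f | no excess in pT1 (k = 0) | half the excess (k = 0.5) | equal excess (k = 1) |
|---|---|---|---|
| 0% | 5.4% | 5.4% | 5.4% |
| 10% | 8.2% | 6.7% | 5.4% |
| 20% | 12.1% | 8.2% | 5.4% |
| 30% | 17.2% | 10.0% | 5.4% |

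At one-sided 2.5% the k = 0 column is 2.7%, 4.4%, 6.9% and 10.4%.

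**3. Imbalance between arms.** Assume a pT1 complication rate of 10% in both arms and T2-T4a rates of 30% and 15%.
- pT1 share 20% robotic, 5% laparoscopic: 0.8 × 30% + 0.2 × 10% = 26.0% against 0.95 × 15% + 0.05 × 10% = 14.75%. False non-inferiority is 14.6%.
- Shares reversed: 0.95 × 30% + 0.05 × 10% = 29.0% against 0.8 × 15% + 0.2 × 10% = 14.0%. The excess is again 15 points and the figure is 5.4%.

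The result depends on the direction of the imbalance.

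**4. The upper end.** The documents give no pT4b or M1 share and no complication rate for these patients, so only the leverage of single patients can be shown. An arm of 68 at 15% has about 10 events (0.15 × 68 = 10.2). Removing one patient with a complication takes 10/68 = 14.7% to 9/67 = 13.4%. Removing two gives 8/66 = 12.1%, a shift of 2.6 points against a 15-point margin.

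**5. Precision in pT2-T4a.** With pT1 shares of 20% and 30%, 68 becomes 54 and 48 per arm (54.4 and 47.6). Exact power at one-sided 5% is then about 72% and 67%.

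**The case against.** The strongest reply is that eligibility is clinical. With the Summary, section 4.1 and section 9.1.2 beside it, section 6(3) describes preoperative stage. A cT2 patient who proves to be pT1 was properly enrolled and had the protocol operation, so keeping that patient is correct. This stands. A reader might infer that pT1 patients breach the protocol's own definition of its subjects and should be removed; the documents do not support that.

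Secondly, the asymmetry has a partial reason. Some withdrawals concern patients in whom the planned curative operation cannot go ahead, and section 9.3.1.11 suspends the study approach for exclusions recognised during the operation. A pT1 patient can have the full procedure. But this does not explain removing T4b or M1 that comes to light only after the operation is complete.

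Thirdly, the larger error rates rest on assumed pT1 shares and on an excess that vanishes in pT1. Nothing in the documents points to either. This also stands, and it is why the table shows k = 0.5 and k = 1.

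Fourthly, the annex treats cytology as part of staging, so lavage may be routine at this centre. The protocol does not say that it is omitted in some patients; it only fails to require it.

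Finally, a stage-based sensitivity analysis could be placed in a statistical analysis plan that is not shown. The withdrawal criteria and the definition of study subjects, however, are fixed in the protocol.

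**Conclusion.** The point holds as an inconsistency in how the analysed population is fixed. Entry is on clinical stage, but stage found at or after surgery is then used to remove patients at the upper end only, in an open, non-randomised study analysed per-protocol. This can shift the set toward easier cases and can do so unequally by arm.

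The size of any effect cannot be taken from the documents. At pT1 shares of 10-30%, false non-inferiority for locally advanced disease ranges from no change (5.4%, equal excess in pT1), through 7-10% (half the excess), to 8-17% (no excess). Imbalance between arms may or may not add to this, according to its direction.

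Two stronger readings go too far. The comparison is not shown to be biased toward non-inferiority: that is conditional on a smaller excess in pT1 or on an unfavourable imbalance. Nor does it follow that pT2-T4a should be the primary set, since that would add another post-surgery exclusion to a non-randomised comparison.

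The per-protocol set also cannot be called the only population in the document while sections 8.1 and 8.1.2 count all operated patients and section 10.1 names a safety population. Those passages need reconciling. The point merits a change to the plan but does not invalidate the design.

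**What to change.** 1. **Sections 6(3) and 4.1:** state that stage eligibility is clinical (cT2-4a, N0/+, M0).
2. **Sections 4.3 and 10.1:** for the 30-day morbidity analysis, do not remove a patient who had the study operation because of a stage found only afterwards (pT4b, or M1 on postoperative pathology or lavage cytology). Reconcile this with the all-operated denominator in sections 8.1 and 8.1.2.
3. **Section 10.1:** prespecify the risk difference and its confidence interval in pT2-T4a M0 as a sensitivity analysis, and report pT1, pT4b and M1 counts by arm.

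**Cost.** Wording and one extra run of the primary analysis. Annex 16.2.5 already provides for pathological T, but the pathology list in section 9.3.4 does not name depth of invasion, so check that the case report form captures it. The primary set will include a few patients outside pT2-T4a. The sensitivity estimate will have fewer patients and a wider interval, with the power shown in step 5 if the pT1 share is as high as 20-30%.

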7.1 Basic principle

All candidate surgeons in this study met the following criteria:

- (1) Performed at least 30 robotic radical total gastrectomies.
- (2) Performed at least 50 laparoscopic radical total gastrectomies.

8. End point and definition of related result determination

8.1 Incidence of operative complications

The number of all patients treated with surgery as the denominator and the number of the patients with any intraoperative and postoperative complications as the numerator are used to calculate the proportions. The criteria for the intraoperative complications refer to the descriptions of intraoperative complications in the observation project (in 9.3.3).

8.1.1 Incidence of intraoperative complications

With the number of patients undergoing surgery as the denominator, the number of patients with any of the following intraoperative complications is calculated as numerator. Intraoperative complications are based on the intraoperative complications mentioned in the intraoperative observations.

8.1.2 Incidence of postoperative complications

The number of all patients treated with surgery as the denominator and the number of the patients with any intraoperative and postoperative complications as the numerator are used to calculate the proportions.

8.1.3 Incidence of overall postoperative complications: The postoperative complication criteria refer to short-term complications after surgery in the postoperative observation project. The time is defined as within 30th after surgery, or the first discharge time if the days of hospital stay more than 30 days.

8.1.4 Incidence of postoperative major complications: The standard for postoperative major complications refers to the short-term complications in the postoperative observation project. according to the Clavien–dindo grade, IIIA level and above for serious complications, and when multiple complications occur simultaneously, the highest ranked complication is the subject.

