9.3.2 Operative parameters (same for both groups)

Completed by the research assistant on the day of the operation. specific projects include:

- (1) Name of responsible surgeons
- (2) Operation time (min)
- (3) Type of operation, digestive tract reconstruction, intraoperative damage and whether the tumor was ruptured during surgery (intact rupture of the capsule)
- (4) Length of incision (cm)
- (5) Conversion to open surgery or not and the reasons for this decision
- (6) Intraoperative estimated blood loss (ml; from skin cutting to stitching, intraoperative blood loss = (postoperative gauze weight, grams - preoperative gauze weight, grams) *1ml/g+ suction fluid, ml)
- (7) Blood transfusion (ml): in this study, the blood transfusion event is defined as transfusion of red cell suspension (ml) or whole blood (ml)
- (8) Tumor location
- (9) Tumor size (maximum tumor diameter, mm)
- (10) Number of lymph nodes dissected in each group and distant metastasis (location)
- (11) Proximal resected margin (mm), distal resected margin (mm), radicality(R0/R1/R2)
- (12) Intraoperative complications (occurring from skin incision to skin closure) including:

surgery-related complications: intraoperative hemorrhage and injury: A. Vascular injury: A vascular injury is defined as a blood vessel with either a blood vessel clamp or a titanium clamp closure and an intra-cavity suture or any other method to control the bleeding. B. Organ damage: maybe including diaphragmatic injury, esophageal injury, duodenal injury, colon injury, small intestine injury, spleen injury (excluding <1/3 spleen ischemia), liver injury, pancreatic injury, gallbladder injury, kidney damage etc.

C. Tumor rupture: tumor envelope Integrity damage

air abdominal-related complications: high-blood carbonate, mediastinal emphysema, subcutaneous emphysema, air embolism, respiratory circulation instability caused by abdominal pressure.

Anesthesia-related complications: Allergic reactions.

(13) Intraoperative death (occurring during the time period from skin cutting to skin stitching completion) regardless of reason.

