9.3.4 Postoperative observation items

Definition of "postoperative day n": One day from 0:00 to up to 24:00. Up to 24:00 on the day of surgery is "postoperative day 0;" the next day from 0:00 to up to 24:00 is "postoperative day 1;" and so on. From the first postoperative day until hospital discharge, the research assistant should timely fill in the following items and specific observation items including:

(1) Pathologic results:

Original lesion tissue typing, Distant metastasis, and parts, NIH Hazard grading, Radical surgery degree (R0/R1/R2), The total number of lymph nodes, the number of lymph nodes in each group, the number of lymph node metastases in each group and the total number of metastases in pathological specimens were obtained

(2) Postoperative complications :

Postoperative complications are divided into and short-term complications after surgery and long-term complications after surgery. Short-term is defined as within 30 days of surgery or the first discharge if the hospital days > 30 days. Long-term is defined as the period from 30 days or more after the operation, or the first discharge (the hospital days after surgery >30 days) to 3 years after the operation.

Severity of complication is graded according to Clavien–dindo complication scoring system,¹⁹

IIIA level and above are serious complication

I: Any deviation from the normal postoperative course without the need for pharmacologic treatment or surgical, endoscopic, and radiologic interventions. Allowed therapeutic regimens are drugs as antiemetics, antipyretics, analgesics, and diuretics, and electrolytes and physiotherapy. This grade also includes wound infections opened at the bedside.

II: Requiring pharmacologic treatment with drugs other than such allowed for grade I complications. Blood transfusions and total parenteral nutrition are also included.

III: Requiring surgical, endoscopic, or radiologic intervention

IIIa: Intervention not under general anesthesia

IIIb: Intervention under general anesthesia

IV : Life-threatening complication (including CNS complications) requiring IC(intermediate care)/ICU(intensive care unit) management

IVa: Single organ dysfunction (including dialysis)

IVb: Multiple organ dysfunction

V: Death as a result of complications

Classification and name of complication	Diagnostic criteria
Abdominal bleeding	Intra-abdominal hemorrhage requires blood transfusion, emergency endoscopy or surgical intervention to eliminate anastomotic bleeding

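### Section 8.1.2 counts intraoperative complications in the postoperative complication rate, contradicting the primary outcome and merging it with a separate secondary outcome

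*Protocol*

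**What the plan says.** Section 5.1 of the protocol names the primary outcome as "Overall postoperative morbidity rates". Section 5.2 lists "Intraoperative morbidity rate" first among the secondary outcomes. Section 8 then says how the rates are formed:

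- **8.1, operative complications:** "the number of the patients with any intraoperative and postoperative complications as the numerator are used to calculate the proportions", over all patients treated with surgery.
- **8.1.1, intraoperative complications:** "the number of patients with any of the following intraoperative complications is calculated as numerator", over patients undergoing surgery.
- **8.1.2, postoperative complications:** "the number of the patients with any intraoperative and postoperative complications as the numerator", over all patients treated with surgery.
- **8.1.3, overall postoperative complications:** "The postoperative complication criteria refer to short-term complications after surgery in the postoperative observation project", with a 30-day window, or up to first discharge for longer stays. No numerator or denominator is given.

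Section 9.3 separates the two kinds of event by time. Section 9.3.2 describes "Intraoperative complications (occurring from skin incision to skin closure) including" a list of items. For postoperative complications, Section 9.3.4 states: "Short-term is defined as within 30 days of surgery or the first discharge if the hospital days > 30 days". The sample size in Section 3.3 rests on a control rate of about 15%, described there as a postoperative rate.

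**The concern.** The numerator in 8.1.2 does not match its heading. It is the 8.1 numerator repeated, so two differently named rates are defined as the same quantity and no fraction is left for postoperative events alone. Taken literally, the primary outcome would absorb the whole of a secondary outcome, and the two could no longer be read as separate results.

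The intraoperative list in 9.3.2 is broad. It includes vascular injury, where bleeding controlled by any method qualifies, as well as organ damage, tumour rupture, pneumoperitoneum-related events and allergic reactions. The number of extra patients counted may therefore not be trivial.

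Two things are at stake. The event rate would exceed the 15% used for sizing, so power would be lower than planned. And an open-label, non-randomised study would hold two different readings of its primary numerator, with nothing in the text to settle which applies before the data are seen.

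**Working it through.** **1. The definitions side by side**

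| Section | Heading refers to | Events in the numerator |
|---|---|---|
| 8.1 | operative | intraoperative and postoperative |
| 8.1.1 | intraoperative | intraoperative |
| 8.1.2 | postoperative | intraoperative and postoperative |
| 8.1.3 | overall postoperative | postoperative criteria only; no fraction stated |

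The row for 8.1.2 is the one that does not fit. Reading its *and* as requiring both kinds of event in the same patient does not help: that would drop patients with only a postoperative complication, which also contradicts Section 5.1.

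**2. Reproducing the planned sample size**

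Inputs from Section 3.3: 15% in both groups, margin 15% (taken as an absolute difference), alpha 0.05, power 80%.

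The test is an unpooled Z test for the difference, declaring non-inferiority when (p1 − p2 − 0.15)/SE ≤ −z, with SE = √{[p1(1 − p1) + p2(1 − p2)]/n}. Exact binomial enumeration at one-sided 0.05 gives 68 as the smallest n with power of at least 0.80 (power 0.8003). The stated 68 is reproduced, and it belongs to a postoperative rate of 15%.

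Under a two-sided 95% confidence interval rule (one-sided 0.025), power at 68 is 0.701. That lower starting point comes from the sidedness of the test, not from 8.1.2. Only the further drop from it bears on this point.

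**3. The rate under the literal 8.1.2 numerator**

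The protocol gives no intraoperative rate, so q = 3%, 5% and 10% are assumptions. If intraoperative events are independent of postoperative ones, the combined rate is 1 − 0.85 × (1 − q):

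- q = 0.03: 1 − 0.85 × 0.97 = 0.1755
- q = 0.05: 1 − 0.85 × 0.95 = 0.1925
- q = 0.10: 1 − 0.85 × 0.90 = 0.235

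**4. Exact power at 68 per group, equal rates, margin 0.15**

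| Assumed q | Combined rate | One-sided 0.05 | 95% CI rule |
|---|---|---|---|
| none | 15.0% | 0.800 | 0.701 |
| 3% | 17.6% | 0.754 | 0.644 |
| 5% | 19.3% | 0.727 | 0.612 |
| 10% | 23.5% | 0.668 | 0.548 |

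**5. Sensitivity to overlap**

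If half of the patients with an intraoperative event also had a postoperative one, the combined rate is 0.15 + q/2, that is 16.5%, 17.5% and 20.0%. Power at one-sided 0.05 is then 0.773, 0.755 and 0.716.

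**6. Cross-check by normal approximation**

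At q = 5% the combined rate is 19.3% with independence and 20.0% (0.15 + 0.05) with no overlap. The required number at one-sided 0.05 rises from 71 per group to between 86 and 88. Power at 68 falls from 0.79 to between 0.71 and 0.72. Direction and size agree with the exact figures.

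**The case against.** The strongest reply is that the primary outcome has its own entry. Section 8.1.3 carries the word *overall*, as Section 5.1 does, refers only to complications after surgery and fixes the window. Section 8.1.2 never says that it defines the primary outcome, and Sections 3.3, 5.2, 8.1.1, 9.3.2 and 9.3.4 all point to a postoperative-only reading. On this view 8.1.2 is a copying slip, not an open analytic choice, and the power loss arises only if someone follows it against the rest of the protocol.

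Much of this stands. A slip is the likely explanation, the intent can be inferred, and nothing suggests that anyone meant to keep two options open. The power figures are conditional illustrations, and overlap between the two kinds of event would make the loss smaller.

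It does not remove the error. Section 8.1.3 supplies criteria and a window but no fraction, so a reader who needs one will take it from 8.1.2, where it is wrong. This is a rule stated incorrectly in the protocol, not a detail left for an analysis plan.

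A narrower objection concerns the fix: 9.3.4 also describes long-term complications, so 8.1.2 may have been meant as a general rate with 8.1.3 as its short-term part. That affects where the primary label should sit, not whether the two words should go.

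**Conclusion.** The concern holds: Section 8.1.2 is wrong as written. Its numerator conflicts with its own heading, with the primary and secondary outcomes in 5.1 and 5.2, with the criteria in 8.1.3 and with the rate used for sizing. This conclusion needs no assumption about event rates.

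The size does. For assumed intraoperative rates of 3% to 10%, independent of postoperative events, following 8.1.2 would cost about 5 to 13 percentage points of power at one-sided 0.05 (0.800 to 0.754 and 0.668), and about 6 to 15 points under a 95% confidence interval rule (0.701 to 0.644 and 0.548). With half of the intraoperative cases overlapping, the one-sided loss is about 3 to 8 points (0.800 to 0.773 and 0.716). Because the intent can be inferred, the study is not invalidated, but the wording should be corrected before analysis.

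**What to change.** In Section 8.1.2, delete the words *intraoperative and*. The numerator then becomes patients with at least one short-term postoperative complication, using the 8.1.3 window (within 30 days, or to first discharge if the stay is longer), over the denominator already given. State that this rate is the primary outcome of Section 5.1. If 8.1.2 is meant as a general rate that also covers long-term events, put the fraction and the primary label in 8.1.3 instead. Keep the combined rate of 8.1 as a separate descriptive measure, and the intraoperative rate of 8.1.1 as the secondary outcome.

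The cost is two deleted words and a sentence or two of clarification. No new data, visits or patients are needed. The planned 68 per group is unaffected, because it was derived from a postoperative rate.
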